4.4.1.3 Supportive Analyses

Not Applicable

4.4.2 Secondary Efficacy Variables

The secondary efficacy variable is same as the primary efficacy variable.

4.5 Analysis of Secondary Objectives

4.5.1 Efficacy

The hypothesis is that the test products will reduce stain to a similar or greater extent than the reference products.

Two comparisons of interest will be done under the secondary objectives. These comparisons are:-

Test Product 1 vs Reference Product 1

Test Product 2 vs Reference Product 2.

The change from baseline in overall MLSI at Week 8 will be analyzed using ANCOVA with treatment as a fixed effect and baseline overall MLSI as a covariate.

From the above ANCOVA model, treatment differences between groups (Test Product 1 vs Reference Product 1 and Test Product 2 vs Reference Product 2), 95% Cis and p-values, will be provided ([Table 14.2.2.2](#)).

The assumption of normality and homogeneity of variance in the ANCOVA model will be investigated. Violation of this assumption will be overcome using a suitable data transformation or a non-parametric technique (e.g. Wilcoxon Rank Sum test).

| | | | | |
|---|------------------|--|---------------------|----------------|
|  GlaxoSmithKline | Document Name | gsk-208078-reporting-and-analysis-plan.pdf | | |
| | Type | Version | Document Identifier | Effective Date |
| | elido_controlled | 0.1, CURRENT; Most-Recent; In Review | 090032d580f4eeeb | |
| | Reason For Issue | | | |

Potassium Nitrate / Sodium Fluoride

208078

Final Statistical Reporting and Analysis plan Amendment 21NOV2017

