This clinical study will compare an experimental low abrasivity 0.5% spherical silica dentifrice and a marketed low abrasivity 6% standard abrasive dentifrice, and an experimental moderate abrasivity 1% spherical silica / 5% STP dentifrice and a marketed high abrasivity 16% standard abrasive silica / 5% STP dentifrice. The main aims of this study are to determine whether spherical silica can achieve similar or greater extrinsic dental stain and plaque removal, in comparison to dentifrices containing higher concentrations of standard abrasive silica, and how the addition of 5% STP enhances cleaning capability. This study has not been designed to demonstrate the specific contribution that spherical silica or STP, are having on the overall reduction of stain and plaque.

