
 To evaluate the ranking order in extrinsic dental stain removal, as measured by overall MLSI Area (A), of a 0.5% spherical silica dentifrice, a marketed 6% abrasive silica dentifrice, a 1% spherical silica / 5% STP dentifrice, and a marketed 16% abrasive silica / 5% STP dentifrice, after 2, 4 and 8 weeks twice daily brushing. 	
 Change from baseline in overall MLSI Area at 2, 4 and 8 weeks.

 To evaluate the ranking order in extrinsic dental stain removal, as measured by overall MLSI Intensity (I), of a low abrasivity 0.5% spherical silica dentifrice, a marketed low abrasivity dentifrice, a moderate abrasivity 1% spherical silica / 5% STP dentifrice, and a marketed higher 	
 Change from baseline in overall MLSI Intensity at 2, 4 and 8 weeks.

GlaxoSmithKline Consumer Healthcare Confidential

Template Version Effective: 22-Jun-2017

Page 19 of 61

Document Name	003270876tprotocol.pdf	Document Identifier	Effective Date
Type	Version		
eldo_clinicalelbc	0.0. DIFFERENT MESSAGING CURRENT	1090032d580fb904bc	14-Aug-2017 09:06:22

Potassium Nitrate / Sodium Fluoride

208078

Final 1.0 Clinical Protocol

abrasivity 5% STP whitening dentifrice, after 2, 4 and 8 weeks twice daily brushing.	
Safety	

 To evaluate the safety and oral tolerability of the test dentifrices when used twice daily for 8 weeks. 	
 Adverse Events

This is a POP study designed to look at the relative extrinsic dental stain and plaque removal performance for all test dentifrices. However, we would expect the following rank order in overall MLSI (A×I) to be observed: the 1% spherical silica / 5% STP dentifrice \geq 16% abrasive silica / 5% STP dentifrice \geq 0.5% spherical silica dentifrice \geq 6% abrasive silica dentifrice.

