10.2 Statistical Methods and Analytical Plan

Additional details of the proposed statistical analysis will be documented in the statistical analysis plan (SAP), which will be written following finalization of the protocol and prior to study unblinding as appropriate.

Treatment differences in the study variables will be tested with the null hypothesis:

H0: there is no treatment difference versus the alternate hypothesis

H1: there is a treatment difference.

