10.2.2 Primary Analysis(es)

The primary efficacy variable is the change from baseline in overall MLSI score. The primary time-point is 8 weeks.

GlaxoSmithKline Consumer Healthcare Confidential

Template Version Effective: 22-Jun-2017

Page 50 of 61

 GlaxoSmithKline	Document Name	003208076ClinicalProtocol.pdf	Document Identifier	Effective Date
	Type	Version		
	eldo_clinicalellbc	0.0. DIFFERENT MESSAGING CURRENT	090032d580fb904c	14-Aug-2017 09:06:22
	Reason For Issue	Auto Issue		

Potassium Nitrate / Sodium Fluoride

208078

Final 1.0 Clinical Protocol

The overall MLSI (AxI) for each subject is derived at a tooth site level first before averaging over all the teeth sites assessed. The change from baseline is derived from the individual sites first before calculating the average change across the sites assessed.

The change from baseline in overall MLSI will be analysed using analysis of covariance (ANCOVA) with treatment as a fixed effect and baseline overall MLSI as a covariate.

The assumption of normality and homogeneity of variance in the ANCOVA model will be investigated. Violation of this assumption will be overcome using a suitable data transformation or a non-parametric technique (eg Wilcoxon Rank Sum test or Van Elteren Test).

There are no comparisons for the primary objective as the main objective is to look at the rank order of the treatments in level of stain reduction after 8 weeks of treatment. This will be achieved via the adjusted means and confidence intervals for the means along with plots of MLSI over time. The hypothesis is that the test products will reduce stain to a greater extent than the reference products.

Two comparisons of interest will be done under secondary and exploratory objectives. These comparisons are: -

Test Product 1 vs Reference Product 1

Test Product 2 vs Reference Product 2.

Analyses at weeks 2 and 4 form part of the exploratory objectives.

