10.2.6 Definition of Analysis Populations

All assessments of safety will be based on the safety population, defined as all subjects who are randomized and receive at least one dose of study treatment during the study. Safety population summaries will be presented by treatment received.

The primary population for efficacy assessment will be the intent-to-treat (ITT) population, defined as all subjects who are randomized, receive the study treatment at least once and provide at least one post-baseline (post treatment) assessment of efficacy. All ITT population summaries and analyses will be presented by treatment randomized.

No Per Protocol population analysis will be performed for this study as it is purely an exploratory Proof of Principal study.

Repeatability population will be defined as any subject who has a repeat stain or plaque assessment. The repeat stain and plaque populations will be separate populations.

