The purpose of this trial is to demonstrate the efficacy and safety of 5% Potassium Nitrate (KNO₃) / Sodium Fluoride (NaF) to treat the symptoms of extrinsic dental stain. Efficacy will be demonstrated through evaluating and comparing the extrinsic dental stain and plaque removal of an experimental low abrasivity 0.5% spherical silica dentifrice and a marketed low abrasivity 6% standard silica abrasive dentifrice, and an experimental moderate abrasivity 1% spherical silica / 5% sodium tripolyphosphate (STP) dentifrice and a marketed high abrasivity 16% standard abrasive silica / 5% STP dentifrice. Safety will be demonstrated through assessment of the incidence of adverse events (AEs).

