1.4 Sample Size Calculation

CCI

A sufficient number of subjects will be screened to randomize at least 124 subjects to ensure 120 evaluable subjects complete the entire study. This will ensure approximately 30 evaluable subjects per treatment arm.

2 Planned Analyses

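### Does the hypothesis of similar or greater stain removal in SAP 4.5.1 need a margin, or a rule for reading a non-significant result?

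*SAP*

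**What the plan says.** Three statements bear on the same pairs (Test Product 1 against Reference Product 1, Test Product 2 against Reference Product 2).

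- SAP Amendment 4.5.1: "The hypothesis is that the test products will reduce stain to a similar or greater extent than the reference products". The October 2017 SAP has the same sentence in substance.
- Protocol 10.2.2: "The hypothesis is that the test products will reduce stain to a greater extent than the reference products".
- Protocol 10.2, for the study variables in general: "H0: there is no treatment difference versus the alternate hypothesis", the alternative being that a difference exists.

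The wider wording is not new in the SAP. Among the main aims in Protocol Section 1 is to "determine whether spherical silica can achieve similar or greater extrinsic dental stain and plaque removal". In Protocol Section 2 the sentence beginning "we would expect the following rank order in overall MLSI" sets out a chain of greater-than-or-equal relations.

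For each pair, SAP 4.5.1 provides an ANCOVA treatment difference, a 95% CI and a p-value. The template for Table 14.2.2.2 fixes the sign, so that a negative difference favours the test product. SAP 4.4.1.2 makes no comparisons for the primary objective, which is read from adjusted means; Addendum 1 confirms that use. The sample-size rationale is redacted in both documents.

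**The concern.** As worded, the SAP hypothesis has the form of a non-inferiority claim, but the planned p-value tests a difference of zero. That test can point to better or to worse; it cannot support *similar*. With no visible margin, no definition of similar and no statement on how to read p > 0.05, an inconclusive comparison is compatible with the hypothesis and could be written up as confirming it. The two documents also word the expectation differently, and the SAP's table of changes from the protocol (Section 5) is silent on the difference.

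At stake is a claim that a less abrasive product cleans as well as its reference when the data cannot exclude a sizeable deficit.

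**Working it through.** **The plan's own figure.** SAP 1.4 gives 124 randomized and 120 evaluable: "This will ensure approximately 30 evaluable subjects per treatment arm". The arithmetic agrees: 120/4 = 30 evaluable per arm, 124/4 = 31 randomized per arm, and an implied loss of 4/124 = 3.2%. The number itself cannot be re-derived because its inputs are redacted.

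**Assumptions.** Thirty evaluable per arm; two-sided 5% level (not stated in visible text, taken to match the 95% CI); differences in units of the residual standard deviation, because no planning SD is visible.

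**Precision.** The ANCOVA has four arms and one covariate, so df = 120 − 4 − 1 = 115. The standard error of a pairwise difference is √(2/30) = 0.258 SD. With t(0.975; 115) = 1.981, the CI half-width is 1.981 × 0.258 = 0.51 SD. It is 0.53 SD with 28 per arm and 0.50 SD with 31.

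**How often a worse product is non-significant.** For a true deficit d, the noncentrality is δ = d/0.258, and P(non-significant) = F(1.981; 115, δ) − F(−1.981; 115, δ), where F is the noncentral t distribution function.

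| True deficit | 30 per arm | 28 to 31 per arm | 30 per arm, 10% level |
|---|---|---|---|
| 0.3 SD | 79% | 80% to 78% | 69% |
| 0.5 SD | 52% | 54% to 50% | 39% |
| 1.0 SD | 3% | not run | not run |

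So p > 0.05 says little about similarity at this size.

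**What the planned CI adds.** With no true difference, the chance that the upper 95% limit excludes a deficit m is 1 − F(1.981; 115, m/0.258): 21% for m = 0.3 SD, 48% for 0.5 SD, 80% for 0.73 SD and 97% for 1.0 SD. The interval is wide, but it shows the reader directly which deficits remain possible.

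**What a margin would have needed.** For 80% power at one-sided 2.5% and no true difference, n per arm = 2(1.960 + 0.842)²/m². This gives 175 for m = 0.3 SD and 63 for m = 0.5 SD. Thirty per arm fits only a margin of about 0.7 SD.

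**The statements side by side.** Protocol 10.2 supplies the null and alternative. SAP 4.5.1 attaches no null, alternative or decision rule to its sentence, so that sentence reads as an expectation. An expectation of similar or greater can sit beside a two-sided test of no difference. In the rank order of Protocol Section 2, each test product stands directly above its own reference with a greater-than-or-equal sign. SAP 4.5.1 therefore matches the protocol's aim and expected order; the sentence in Protocol 10.2.2 is the narrower one.

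**The case for a change.** The best case for a change is that SAP Section 1 uses confirmatory language, "Efficacy will be demonstrated through evaluating and comparing the extrinsic dental stain and plaque removal", and that p-values are planned for these pairs, so their reading should be fixed. A CI without a threshold does not decide whether similar has been met. A sentence saying that non-significance is inconclusive would cost almost nothing and could only restrict claims, so it could not favour the test products.

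Some of this stands. Non-significance is not evidence of similarity here, and the wording difference should ideally have been logged. The rest carries less weight. The Section 1 phrase is loose summary text: the sentence before it describes the trial as showing that potassium nitrate and sodium fluoride treat stain, which is not a listed objective. Protocol 10.2.6 omits a per-protocol analysis "as it is purely an exploratory Proof of Principal study", and no success criterion is visible that these p-values could trigger. The proposed sentence would mostly restate Protocol 10.2 and would leave model, contrasts and tables as they are. Addendum 1 records that its changes followed unblinding, so rewriting a prespecified hypothesis now would itself be post hoc, and a margin chosen now would be worse.

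**Conclusion.** No change to the plan is needed. Followed as written, it produces the right quantities: a signed difference, its 95% CI and a two-sided p-value for each pair. The gap is a reading convention that an analyst supplies as a matter of course, namely to report an inconclusive test as inconclusive and to describe similarity from the interval. The unlogged difference between Protocol 10.2.2 and SAP 4.5.1 is clerical.

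The figures show why the convention matters: a half-width of about 0.51 SD, and 79% and 52% non-significance for true deficits of 0.3 and 0.5 SD. They rest on 30 per arm, an assumed 5% two-sided level and SD units, and they would be the same for any four-arm trial of this size. The visible text does not show which deficit would matter, and a margin may lie in the redacted sample-size text, so its absence from the full plan is not established. The conclusion would differ if the plan treated p > 0.05 as similarity or hung a success claim on it; it does neither. The primary ranking is unaffected.

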4.6 Analysis of Exploratory Objectives

4.6.1.1 Exploratory Efficacy Endpoint Definition

The exploratory variables are;

- Change from baseline in overall interproximal MLSI (AxI) stain score at Weeks 2, 4 and 8
- Change from baseline in overall area (A) stain score at Weeks 2, 4 and 8
- Change from baseline in overall intensity (I) stain score at Weeks 2, 4 and 8
- Change from baseline (pre-treatment) in overall TPI for Day 2 post-treatment, Week 8 pre-treatment and Week 8-post treatment
- Change from baseline (pre-treatment) in interproximal TPI for Day 2 post-treatment, Week 8 pre-treatment and Week 8 post-treatment

All stain variables will be derived in a similar way based on relevant tooth sites. The interproximal stain sites are the mesial and distal tooth sites.

The overall TPI for each subject is derived at a tooth site level first before averaging over all the teeth sites assessed. The change from baseline is derived at the individual sites first before calculating the average change across the sites assessed.

The interproximal TPI is based on the mesial and distal tooth sites. The interproximal TPI score and change from baseline are calculated in the same way as for the overall TPI.

4.6.1.2 Analysis of Exploratory Variables

Summary statistics including mean, SD, median, min, and max will be provided for week 2 and week 4 by randomized treatment group ([Table 14.2.2.1](#)).

All stain variables will be analyzed as per the primary efficacy variable using the appropriate baseline values as a covariate.

The change from baseline in TPI variables will be analyzed using analysis of covariance (ANCOVA) with treatment and MLSI stratification as fixed effects and appropriate baseline (pre-treatment) TPI as a covariate.

From ANCOVA model, the adjusted mean for each treatment group will be provided with 95% Cis and corresponding p-values.

Results for overall interproximal MLSI (AxI) score, overall MLSI area score, overall MLSI intensity score, overall TPI score and overall Interproximal TPI Score will be presented in [Table 14.2.3.1](#), [Table 14.2.3.2](#), [Table 14.2.4.1](#), [Table 14.2.4.2](#), [Table 14.2.5.1](#), [Table 14.2.5.2](#), [Table 14.2.6.1](#), [Table 14.2.6.2](#) and [Table 14.2.7.1](#), [Table 14.2.7.2](#) respectively.

| | | | | |
|---|------------------|--|---------------------|----------------|
|  GlaxoSmithKline | Document Name | gsk-208078-reporting-and-analysis-plan.pdf | | |
| | Type | Version | Document Identifier | Effective Date |
| | elido_controlled | 0.1, CURRENT; Most-Recent; In Review | 090032d580f4eeeb | |
| | Reason For Issue | | | |

Potassium Nitrate / Sodium Fluoride

208078

Final Statistical Reporting and Analysis plan Amendment 21NOV2017

4.6.2 Handling of Missing Values/Censoring/Discontinuations

Missing data will not be replaced or imputed. Dropouts will be included in analyses up to the point of discontinuation.

4.7 Analysis of Safety

4.7.1 Adverse Events and Serious Adverse Events

All summaries of safety will be performed using the safety population and will be analyzed based on treatment actually received. No formal statistical testing will be performed on summary comparisons related to safety related measurements.

All Aes will be coded using the medical dictionary for regulatory activities (MedDRA). Aes will be classified by system organ class (SOC) and by preferred term (PT). In addition, prior to database lock all Aes will be reviewed by the Clinical Research Director (or designee) and categorized as either oral or non-oral. Safety will be assessed based on any oral Aes (this includes those that are identified as treatment emergent oral soft tissue (OST) abnormalities and spontaneously reported oral Aes). Any new or worsening OST condition that occurs after the OST examinations at Screening will be recorded as an AE.

Aes will be summarized using descriptive statistics (frequency tables) by treatment group. Summary tables will indicate both the number of events and the number (percent) of subjects involved. Summaries of Aes will include only treatment emergent adverse events (TEAEs) unless otherwise noted. TEAEs are defined as new Aes that occur on or after the date/time of the first supervised use of the randomized treatment (or events aggravated in severity following treatment). Events with an onset date/time prior to first use of a treatment will be considered as non-treatment emergent. Listing of Aes (including non-treatment emergent from All Subjects) will be provided.

The following summary tables and listings will be presented by treatment group.

- Table of treatment emergent Aes by SOC and Preferred Term ([Table 14.3.1.1.1](#))
- Table of treatment emergent Aes by Oral/Non-Oral and Preferred Term ([Table 14.3.1.1.2](#))
- Table of treatment emergent treatment related Aes by SOC and Preferred Term ([Table 14.3.1.3.1](#))
- Table of Treatment emergent treatment related Aes by Oral/Non-Oral and Preferred Term ([Table 14.3.1.3.2](#))
- Table of Non-serious treatment emergent Aes by SOC and PT (only produced if there are more than 5 SAEs) ([Table 14.3.1.4](#))

GlaxoSmithKline Consumer Healthcare Confidential

Page 16 of 53

| | | | | |
|---|------------------|--|---------------------|----------------|
|  GlaxoSmithKline | Document Name | gsk-208078-reporting-and-analysis-plan.pdf | | |
| | Type | Version | Document Identifier | Effective Date |
| | elido_controlled | 0.1, CURRENT; Most-Recent; In Review | 090032d580f4eeeb | |
| | Reason For Issue | | | |

Potassium Nitrate / Sodium Fluoride

208078

Final Statistical Reporting and Analysis plan Amendment 21NOV2017

- Listing of all AEs (including all subjects: [Listing 16.2.7.1.1](#) for all randomized subjects; [Listing 16.2.7.1.2](#) for non-randomized subjects)
- Listing of death ([Listing 14.3.2.1](#))
- Listing of non-fatal SAEs ([Listing 14.3.2.2](#))
- Listing of treatment emergent AEs leading to withdrawal ([Listing 14.3.2.3](#))
- Listing of treatment emergent AEs classified as oral ([Listing 14.3.2.4](#))

In the event that there is nothing to report a null listing will be produced.

4.7.2 Other Safety Variables

All incidents captured in the study will be listed ([Listing 16.2.7.2](#)). Oral soft issue data will be listed ([Listing 16.2.7.3](#)). All eCRF comments will be listed ([Listing 16.2.3](#)).

4.8 Analysis of Other Variables

To assess the repeatability of the stain and TPI assessments, replicate examinations will be performed by the same qualified dental examiner at each assessment visit. Five subjects will be randomly selected for repeat MLSI and TPI assessments across each assessment window.

The repeat stain and plaque assessments will be compared to the original assessments and will not be used in any efficacy analysis. The first and second assessments on each tooth site will be cross tabulated. A weighted Kappa coefficient (κ), along with the 95% CI will be calculated to assess the intra-examiner reliability. Fleiss-Cohen weighted kappa will be calculated for the repeatability analysis. Reliability will be deemed

- Excellent if $\kappa > 0.75$
- Fair to good if $0.4 \leq \kappa \leq 0.75$
- Poor if $\kappa < 0.4$

All subjects who have repeatability data will be included in this analysis. Results for repeat MLSI area and intensity assessments will be in [Table 14.2.8.1](#) and [Table 14.2.8.2](#) respectively. Also result for repeat TPI assessment will be [Table 14.2.8.3](#).

5 Changes to the Protocol Defined Statistical Analysis Plan

Changes from the originally planned statistical analysis specified in the protocol are outlined in Table 1.

Table 1 Changes to Protocol Defined Analysis Plan

| Protocol | Reporting & Analysis Plan | |
|------------------------------|---------------------------|-----------------------|
| Statistical Analysis section | Statistical Analysis Plan | Rationale for Changes |

GlaxoSmithKline Consumer Healthcare Confidential

Page 17 of 53

| | | | |
|------------------|--|---------------------|----------------|
| Document Name | gsk-208078-reporting-and-analysis-plan.pdf | | |
| Type | Version | Document Identifier | Effective Date |
| elido_controlled | 0.1, CURRENT; Most-Recent; In Review | 090032d580f4eeeb | |
| Reason For Issue | | | |

Potassium Nitrate / Sodium Fluoride

208078

Final Statistical Reporting and Analysis plan Amendment 21NOV2017

| Protocol | Reporting & Analysis Plan | |
|---|--|---|
| Statistical Analysis section | Statistical Analysis Plan | Rationale for Changes |
| 
 Section 10.2.1: Descriptive statistics (number of subjects, mean, standard deviation, median, minimum and maximum for continuous variables, and frequency and percentage for categorical variables) will be provided for demographic baseline characteristics concomitant medication, medical history and compliance. | 
 We are not providing descriptive statistics for concomitant medications, medical histories and compliance. | 
 Summary tables are not required for reporting |
| 
 10.2.4- Safety Analysis(es) Listing of SAEs (if there are none a null listing will be produced; if there are more than 5 treatment emergent SAEs a table will be produced instead by SOC and PT) | 
 Analysis of Safety Listing of death (Listing 14.3.2.1); Listing of non-fatal SAEs (Listing 14.3.2.2) | 
 As per RAP template and list of required TLF list for Oral studies, two listings have been added in RAP. |
| 
 10.2.6 Definition of Analysis Populations | 
 We have added two populations in RAP which are all screened subjects and randomized population. | 
 We will require these population for some TLFs. |
| 
 Safety Analysis(es) | 
 The below table is not included in the RAP: Treatment emergent Aes by Intensity presented by System Organ Class (SOC) and PT | 
 It is not required since it is study dependent and not required for this study. |
| 
 10.2.6 Definition of Analysis Populations | 
 We have added two subsets population for repeatability population in RAP. | 
 It is not possible to keep the repeated subjects for stain and plaque assessment under the same population. Therefore we have developed subset population for MLSI and TPI repeatability. |

| | | | |
|------------------|--|---------------------|----------------|
| Document Name | gsk-208078-reporting-and-analysis-plan.pdf | | |
| Type | Version | Document Identifier | Effective Date |
| elido_controlled | 0.1, CURRENT; Most-Recent; In Review | 090032d580f4eeeb | |
| Reason For Issue | | | |

Potassium Nitrate / Sodium Fluoride

208078

Final Statistical Reporting and Analysis plan Amendment 21NOV2017

6 Abbreviation

| Abbreviation | Term |
|------------------|---|
| AE | adverse event |
| TEAE | treatment-emergent adverse event |
| ANCOVA | analysis of covariance |
| CI | confidence interval |
| ITT | intent-to-treat |
| KNO ₃ | potassium nitrate |
| NaF | sodium fluoride |
| STP | sodium tripolyphosphate |
| MedDRA | medical Dictionary for Regulatory Activities |
| MLSI | Macpherson modification of the Lobene Stain Index |
| OST | oral soft tissue |
| SAE | serious adverse event |
| SOC | system organ class |
| PT | preferred term |
| TPI | Turesky modification of the Quigley Hein Index |
| A | Area |
| I | Intensity |
| SD | standard deviation |
| Med | median |
| Min | minimum |
| Max | maximum |
| RLR | review listing requirement |
| BDRM | blinded data review meeting |
| SAS | statistical analysis system |
| GSK CH | GlaxoSmithKline Consumer Healthcare |
| POP | proof of principle |

GlaxoSmithKline Consumer Healthcare Confidential

Page 19 of 53

| | | | |
|------------------|--|---------------------|----------------|
| Document Name | gsk-208078-reporting-and-analysis-plan.pdf | | |
| Type | Version | Document Identifier | Effective Date |
| elido_controlled | 0.1, CURRENT; Most-Recent; In Review | 090032d580f4eeeb | |
| Reason For Issue | | | |

Potassium Nitrate / Sodium Fluoride

208078

Final Statistical Reporting and Analysis plan Amendment 21NOV2017

7 Attachment 1: List of Data Displays

Study 208078_List of Outputs.xlsx

| | | | |
|------------------|--|---------------------|----------------|
| Document Name | gsk-208078-reporting-and-analysis-plan.pdf | | |
| Type | Version | Document Identifier | Effective Date |
| elido controlled | 0.1; CURRENT; Most-Recent; In Review | 090032d580f4eeeb | |
| Reason For Issue | | | |

Potassium Nitrate / Sodium Fluoride

208078

Final Statistical Reporting and Analysis plan Amendment 21NOV2017

8 Appendix 1: Template for Tables, Figures and Listings

This is a guideline which will give the guidance of treatment labels that will be used for the table header and in the figures, listings and in the footnotes.

The treatment labels for the column heading will be as follow:

- Test Product 1
- Test Product 2
- Reference Product 1
- Reference Product 2

The treatment comparison will be in below order;

Test Product 1 Vs Test Product 2

Reference Product 1 Vs Reference Product 2

The below footnotes will be used for each outputs;

Test Product 1: 5% KNO₃ / 0.2542% NaF dentifrice with 0.5% spherical silica (RDA~38)

Test Product 2: 5% KNO₃ / 0.2542% NaF dentifrice with 1% spherical silica and 5% STP (RDA~58)

Property of GSK Consumer Healthcare
Confidential

May not be used, divulged, published or otherwise disclosed
without the consent of GSK

Template Version Effective: 15-Jul-2017

Page 21 of 53

| | | | |
|------------------|--|---------------------|----------------|
| Document Name | gsk-208078-reporting-and-analysis-plan.pdf | | |
| Type | Version | Document Identifier | Effective Date |
| elido controlled | 0.1; CURRENT; Most-Recent; In Review | 090032d580f4eeeb | |
| Reason For Issue | | | |

Potassium Nitrate / Sodium Fluoride

208078

Final Statistical Reporting and Analysis plan Amendment 21NOV2017

Reference Product 1: Sensodyne Pronamel Daily Protection (RDA~36).

Reference Product 2: Sensodyne Extra Whitening (RDA~166).

GlaxoSmithKline Consumer Healthcare Confidential
Page 22 of 53

| | | | |
|------------------|--|---------------------|----------------|
| Document Name | gsk-208078-reporting-and-analysis-plan.pdf | | |
| Type | Version | Document Identifier | Effective Date |
| elido controlled | 0.1; CURRENT; Most-Recent; In Review | 090032d580f4eeeb | |
| Reason For Issue | | | |

Potassium Nitrate / Sodium Fluoride

208078

Final Statistical Reporting and Analysis plan Amendment 21NOV2017

Protocol 208078

Program Run Date: DDMMYYYY

Table 14.1.1
Subject Disposition
All Screened Subjects

Study Population: All Screened Subjects (N=xxx)

| | Test Product 1 N (%) | Test Product 2 N (%) | Reference Product 1 N (%) | Reference Product 2 N (%) | Overall N (%) |
|-----------------------------|-------------------------|-------------------------|------------------------------|------------------------------|------------------|
| TOTAL SUBJECTS SCREENED | | | | | xxx |
| SUBJECTS NOT RANDOMIZED | | | | | xxx (xx.x) |
| DID NOT MEET STUDY CRITERIA | | | | | xxx (xx.x) |
| ADVERSE EVENT | | | | | Xxx (xx.x) |
| LOST TO FOLLOW UP | | | | | xxx (xx.x) |
| PROTOCOL VIOLATION | | | | | Xxx (xx.x) |
| WITHDRAWAL OF CONSENT | | | | | Xxx (xx.x) |
| OTHER | | | | | Xxx (xx.x) |
| SUBJECTS RANDOMIZED | xxx | xxx | xxx | xxx | xxx |
| COMPLETED STUDY | xxx (xx.x) | xxx (xx.x) | xxx (xx.x) | xxx (xx.x) | xxx (xx.x) |
| DID NOT COMPLETE STUDY | xxx (xx.x) | xxx (xx.x) | xxx (xx.x) | xxx (xx.x) | xxx (xx.x) |
| DID NOT MEET STUDY CRITERIA | xxx (xx.x) | xxx (xx.x) | xxx (xx.x) | xxx (xx.x) | xxx (xx.x) |
| ADVERSE EVENT | xxx (xx.x) | xxx (xx.x) | xxx (xx.x) | xxx (xx.x) | xxx (xx.x) |
| LOST TO FOLLOW-UP | xxx (xx.x) | xxx (xx.x) | xxx (xx.x) | xxx (xx.x) | xxx (xx.x) |
| PROTOCOL VIOLATION | xxx (xx.x) | xxx (xx.x) | xxx (xx.x) | xxx (xx.x) | xxx (xx.x) |

GlaxoSmithKline Consumer Healthcare Confidential

Page 23 of 53

| | | | |
|------------------|--|---------------------|----------------|
| Document Name | gsk-208078-reporting-and-analysis-plan.pdf | | |
| Type | Version | Document Identifier | Effective Date |
| elido controlled | 0.1; CURRENT; Most-Recent; In Review | 090032d580f4eeeb | |
| Reason For Issue | | | |

Potassium Nitrate / Sodium Fluoride

208078

Final Statistical Reporting and Analysis plan Amendment 21NOV2017

| | Test Product 1 N (%) | Test Product 2 N (%) | Reference Product 1 N (%) | Reference Product 2 N (%) | Overall N (%) |
|-------------------------------|-------------------------|-------------------------|------------------------------|------------------------------|------------------|
| WITHDRAWAL OF CONSENT | xxx (xx.x) | xxx (xx.x) | xxx (xx.x) | xxx (xx.x) | xxx (xx.x) |
| OTHER | xxx (xx.x) | xxx (xx.x) | xxx (xx.x) | xxx (xx.x) | xxx (xx.x) |
| SAFETY POPULATION | xxx (xx.x) | xxx (xx.x) | xxx (xx.x) | xxx (xx.x) | xxx (xx.x) |
| ITT POPULATION | xxx (xx.x) | xxx (xx.x) | xxx (xx.x) | xxx (xx.x) | xxx (xx.x) |
| REPEATABILITY POPULATION | xxx (xx.x) | xxx (xx.x) | xxx (xx.x) | xxx (xx.x) | xxx (xx.x) |
| MLSI REPEATABILITY POPULATION | xxx (xx.x) | xxx (xx.x) | xxx (xx.x) | xxx (xx.x) | xxx (xx.x) |
| TPI REPEATABILITY POPULATION | xxx (xx.x) | xxx (xx.x) | xxx (xx.x) | xxx (xx.x) | xxx (xx.x) |

Percentages for non-randomized category are based on number of screened subjects; percentages for randomized category are based on number of randomized subjects

Page x of y

PPD

| | | | |
|------------------|--|---------------------|----------------|
| Document Name | gsk-208078-reporting-and-analysis-plan.pdf | | |
| Type | Version | Document Identifier | Effective Date |
| elido controlled | 0.1; CURRENT; Most-Recent; In Review | 090032d580f4eeeb | |
| Reason For Issue | | | |

Potassium Nitrate / Sodium Fluoride

208078

Final Statistical Reporting and Analysis plan Amendment 21NOV2017

Protocol 208078

Program Run Date: DDMMYYYY

Table 14.1.2
Incidence of Major Protocol Deviations
All Randomized Population

Study Population: All Randomized Population (N=xxx)

| | Test Product 1 N (%) | Test Product 2 N (%) | Reference Product 1 N (%) | Reference Product 2 N (%) | Overall N (%) |
|--|-------------------------|-------------------------|------------------------------|------------------------------|------------------|
| NUMBER OF SUBJECTS WITH AT LEAST ONE IMPORTANT PROTOCOL DEVIATIONS | xxx (xx.x) | xxx (xx.x) | xxx (xx.x) | xxx (xx.x) | xxx (xx.x) |
| DEVIATIONS 1 | xxx (xx.x) | xxx (xx.x) | xxx (xx.x) | xxx (xx.x) | xxx (xx.x) |
| DEVIATIONS 2 | xxx (xx.x) | xxx (xx.x) | xxx (xx.x) | xxx (xx.x) | xxx (xx.x) |
| DEVIATIONS 3 | xxx (xx.x) | xxx (xx.x) | xxx (xx.x) | xxx (xx.x) | xxx (xx.x) |
| DEVIATIONS 4 | xxx (xx.x) | xxx (xx.x) | xxx (xx.x) | xxx (xx.x) | xxx (xx.x) |
| ... | | | | | |

Page x of y

PPD

| | | | |
|------------------|--|---------------------|----------------|
| Document Name | gsk-208078-reporting-and-analysis-plan.pdf | | |
| Type | Version | Document Identifier | Effective Date |
| elido controlled | 0.1; CURRENT; Most-Recent; In Review | 090032d580f4eeeb | |
| Reason For Issue | | | |

Potassium Nitrate / Sodium Fluoride

208078

Final Statistical Reporting and Analysis plan Amendment 21NOV2017

Protocol 208078

Program Run Date: DDMMYYYY

Table 14.1.3
Analysis Populations
All Randomized Population

Study Population: All Randomized Population (N=xxx)

| | Test Dentifrice (RDA-58) N (%) | Test Dentifrice (RDA-77) N (%) | Reference Dentifrice (RDA-80) N (%) | Reference Dentifrice (RDA-120) N (%) | Overall N (%) |
|---|--------------------------------------|--------------------------------------|---|--|------------------|
| NUMBER OF SUBJECTS EXCLUDED FROM SAFETY POPULATION | xxx (xx.x) | xxx (xx.x) | xxx (xx.x) | xxx (xx.x) | xxx (xx.x) |
| Reason 1 | xxx (xx.x) | xxx (xx.x) | xxx (xx.x) | xxx (xx.x) | xxx (xx.x) |
| Reason 2 | xxx (xx.x) | xxx (xx.x) | xxx (xx.x) | xxx (xx.x) | xxx (xx.x) |
| ... | | | | | |
| NUMBER OF SUBJECTS EXCLUDED FROM ITT POPULATION | xxx (xx.x) | xxx (xx.x) | xxx (xx.x) | xxx (xx.x) | xxx (xx.x) |
| Reason 1 | xxx (xx.x) | xxx (xx.x) | xxx (xx.x) | xxx (xx.x) | xxx (xx.x) |
| Reason 2 | xxx (xx.x) | xxx (xx.x) | xxx (xx.x) | xxx (xx.x) | xxx (xx.x) |
| ... | | | | | |

Page x of y

PPD

[redacted]

| | | | |
|------------------|--|---------------------|----------------|
| Document Name | gsk-208078-reporting-and-analysis-plan.pdf | | |
| Type | Version | Document Identifier | Effective Date |
| elido controlled | 0.1; CURRENT; Most-Recent; In Review | 090032d580f4eeeb | |
| Reason For Issue | | | |

Potassium Nitrate / Sodium Fluoride

208078

Final Statistical Reporting and Analysis plan Amendment 21NOV2017

Protocol: 208078

Program Run Date: DDMMYYYY

Table 14.1.4.1
Demographic and Baseline Characteristics
Safety Population

Study Population: Safety Population (N=xxx)

| | Test Product 1 N (%) | Test Product 2 N (%) | | OVERALL (N=xx) |
|---|-------------------------|-------------------------|---------------------|-------------------|
| SEX N (%) | | | | |
| MALE | XX (XX.X) | XX (XX.X) | ... | XX (XX.X) |
| FEMALE | XX (XX.X) | XX (XX.X) | | XX (XX.X) |
| RACE N (%) | | | | |
| AFRICAN AMERICAN/AFRICAN HERITAGE | XX (XX.X) | XX (XX.X) | ... | XX (XX.X) |
| AMERICAN INDIAN OR ALASKAN NATIVE | XX (XX.X) | XX (XX.X) | | XX (XX.X) |
| ASIAN - CENTRAL/SOUTH ASIAN HERITAGE | XX (XX.X) | XX (XX.X) | | XX (XX.X) |
| ASIAN - EAST ASIAN HERITAGE | XX (XX.X) | XX (XX.X) | ... | XX (XX.X) |
| ASIAN - SOUTH EAST ASIAN HERITAGE | XX (XX.X) | XX (XX.X) | ... | XX (XX.X) |
| NATIVE HAWAIIAN OR OTHER PACIFIC ISLANDER | XX (XX.X) | XX (XX.X) | ... | XX (XX.X) |
| WHITE - ARABIC/NORTH AFRICAN HERITAGE | XX (XX.X) | XX (XX.X) | ... | XX (XX.X) |
| WHITE - WHITE/CAUCASIAN/EUROPEAN HERITAGE | XX (XX.X) | XX (XX.X) | ... | XX (XX.X) |
| ETHNICITY N (%) | | | ... | |
| HISPANIC OR LATINO | XX (XX.X) | XX (XX.X) | | XX (XX.X) |
| NOT HISPANIC OR LATINO | XX (XX.X) | XX (XX.X) | ... | XX (XX.X) |
| AGE (YEARS) | | | ... | |
| N | XX | XX | ... | XX |
| MEAN | XX.X | XX.X | ... | XX.X |
| SD | XX.XX | XX.XX | ... | XX.XX |

GlaxoSmithKline Consumer Healthcare Confidential

Page 27 of 53

| | | | |
|------------------|--|---------------------|----------------|
| Document Name | gsk-208078-reporting-and-analysis-plan.pdf | | |
| Type | Version | Document Identifier | Effective Date |
| elido controlled | 0.1; CURRENT; Most-Recent; In Review | 090032d580f4eeeb | |
| Reason For Issue | | | |

Potassium Nitrate / Sodium Fluoride

208078

Final Statistical Reporting and Analysis plan Amendment 21NOV2017

| | | | | |
|---------------------------|-----------|-----------|-----------|-----------|
| MEDIAN | XX.X | XX.X | | XX.X |
| MINIMUM | XX | XX | | XX |
| MAXIMUM | XX | XX | ... | XX |
| STRATIFICATION | | | | |
| STRATA 1: LOW (MLSI <15) | XX (XX.X) | XX (XX.X) | XX (XX.X) | XX (XX.X) |
| STRATA 2: HIGH (MLSI ≥15) | XX (XX.X) | XX (XX.X) | XX (XX.X) | XX (XX.X) |

